### 10.1.3 Additional recordings

- Cumulative dose and hours of Norepinephrine or other vasopressor infusion.
- Start of epidural (control group only) early/late

## 11 Handling of Adverse Events

All complications and other outcomes will be recorded in the eCRF as described above. No new treatments or drugs are investigated in this trial and thus no adverse event recording or evaluation outside the DSMC evaluations are planned.

Local Anesthetic Systemic Toxicity, LAST

LAST is a very rare condition in which systemic effects from local anesthetics (both epidural and other peripheral use) can cause CNS and cardiac toxicity. It is caused by supratherapeutic plasma concentrations, often caused by an inadvertent intravascular injection. This occurs in less than 1/1000 patients and a recent study observed no cases of LAST in over 9000 peripheral nerve blocks. With the doses used in clinical practice and correct injection technique under direct thoracoscopic vision, risks are very low and treatment, including lipid emulsion injection, is known in all participating centers.

Trial ID:	ISRCTN16853684
Version No:	1.0
Date:	January 27 th 2026

## 12 Independent Data Monitoring and Safety Committee

The Data Monitoring and Safety Committee (DMSC) will be presented with a complete list of complications and other outcomes from each of the two trial arms after 100 and 250 patients have been included in the trial. The DMSC will then at these points in time make an evaluation of patient safety in the trial. The DMSC will, after their assessment, present a brief report to the trial steering committee and, if serious safety issues are detected, actions will be taken to address these. Ultimately, if such serious safety issues cannot be addressed in any other effective way, the trial may be stopped.

## 13 Statistics

### 13.1 Sample size calculation

In a recent Dutch trial, anastomotic leak was present in 13.8 % of the patients with epidural analgesia and 6.1% in those without(9). Recent data from the Nordic countries show a leak rate of 15.2%(2). We therefore base the sample size calculation on the aim of finding a reduction from 15% to 7.5% leak in the intervention group.

With a power (1- $\beta$ ) of 80% and a significance ( $\alpha$ ) of 5%, this would require 275 patients in each group or 550 patients in total.

With some expected drop-outs (e.g., no resection performed due to more advanced disease than anticipated), we expect a total of 600 patients to be randomized.

### 13.2 Prespecified subgroup analyses

Predefined subgroups to be analyzed include gender (male/female), neck anastomosis (y/n), age >75 (y/n), pyloric drainage procedure (y/n) and ASA (<3/>2).

Safety endpoints will be presented using descriptive statistics without any formal comparisons between treatment groups based on the Safety population.

## 14 Data management

### 14.1 Recording of data

Baseline and surgical data will be collected in a study database as pseudonymized data. An eCRF will be used for all mandatory primary and secondary outcomes except survival. All study data will be transferred from the eCRF to the study database. An additional survival sweep will be performed at 3 and 5 years from the local study databases and added to the main study database. Written consent will be stored at each study site and the local study staff is responsible for source documents being accessible for monitoring.

### 14.2 Data storage and management

All data will be recorded, handled, and stored in accordance with Regulation (EU) 2016/679 (General Data Protection Regulation, GDPR), in a way that allows its accurate reporting, interpretation, and verification. All source data, including a copy of the completed study database and the original protocols with amendments will be stored at the Department of Surgical Sciences at Uppsala University Hospital in accordance with Sponsor regulations.

When inclusion is complete, any deviations from the protocol will be recorded. When the study database has been declared complete and accurate, it will be locked and available for analysis.

Trial ID:	ISRCTN16853684
Version No:	1.0
Date:	January 27 th 2026

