## 8.4 Withdrawal criteria

Subjects can discontinue their participation in the trial at any time without any consequence to his/her continued treatment. The investigator/sponsor can at any time terminate the trial for a subject due to, e.g., unacceptable adverse events/adverse reactions or because the subject does not follow procedures in the clinical trial protocol. If the subject discontinues the trial, follow-up of this subject will be performed according to the clinical routine of the study site in question.

Specific reasons for discontinuing a subject for further assessments include:

- Withdrawal of informed consent.
- Not fulfilling the inclusion/exclusion criteria as stated above (incorrectly included).
- No resection performed (reason specified)
- Operation was converted to open surgery
- If the investigator considers it not to be in the subject's best interest to continue participation in the study (e.g. due to non-tolerable adverse reactions or serious adverse events (SAEs) during surgery).
- If there is a significant protocol deviation.

A discontinued subject should be asked to come to the clinic for a final assessment, if possible. The reason for subject discontinuation will be documented in the eCRF. The sponsor has the right to keep and use all data that has been collected up until the time that the subject discontinues study participation. A study subject who has been randomized and who is withdrawn from the study will not be replaced.

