## 9 Trial treatments

### 9.1 Randomization and blinding

Subjects are enrolled and randomized consecutively as they are found to be eligible for inclusion in the trial. Randomization is performed no later than 12h before surgery. If a subject discontinues participation, the subject's trial-specific code will not be reused, and the subject will not be allowed to re-enter the trial.

Randomization will be performed online from within an electronic randomization system, after a multidisciplinary tumor board meeting, once all eligibility criteria have been verified and no exclusion criteria have been fulfilled. Randomization will be stratified by country and level of anastomosis (chest/neck). The electronic randomization module is accessed from each participating site. Treatment

Trial ID: ISRCTN16853684  
Version No: 1.0  
Date: January 27th 2026

allocation will be open-label, among the two intervention arms at a 1:1 ratio of paravertebral block and opioid PCA (intervention) or standard EDA treatment (control).

All randomized trial subjects will be recorded on the Participant Identification Code List, which includes the participant's name and personal identification number, date of informed consent and randomization date. It is the responsibility of the Investigator to keep the list updated throughout the trial and store it in a secure location to prevent unauthorized access.

No blinding will be used during treatment. Statisticians will be blinded at time of analysis after data-lock.

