## 9.5 Escape medication

Patients will be offered patient-controlled analgesia with opioids if EDA pain control is insufficient. Escape (intervention group) or re-insertion (control group) of EDA can also be offered and should be recorded in the eCRF. All opioids given will be recorded.

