# 10 Methods for measurement of endpoints for clinical efficacy and safety

Baseline data will be collected in an electronic randomization module where clinical information and stratification variables will be entered by the site investigator no later than the day before surgery. An eCRF will be filled out for all outcomes at the first postoperative visit, 30 days postop. All study data will be transferred from the eCRF to the study database. Additional outcome data (survival) will be accrued at 3 and 5 years and added to the study database.

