## 10.1 Methods for measurement

### 10.1.1 Primary endpoint

The primary endpoint of anastomotic leak will be assessed according to local routines. A CT with contrast swallow is performed on postoperative day 7. If this CT is not performed (prior CT performed on clinical suspicion or other reason), this is specified. When the eCRF is filled out, all anastomotic leaks up to 30 days will be recorded, including day of onset. The questions regarding the primary outcome will be:

- Anastomotic leak (yes/no)
- Anastomotic leak type (grade I-III according to Low et al.(14))
- Day of a diagnosed anastomotic leak (1-30/NA)

Trial ID:	ISRCTN16853684
Version No:	1.0
Date:	January 27 th 2026

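### Deviation recording is set at the end of inclusion (14.2), which does not fit deviation-based discontinuation (8.4); 8.4 in turn conflicts with the ITT rule (13.3)

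*Protocol*

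**What the plan says.** Section 14.2, just before its sentence on database lock, states: "When inclusion is complete, any deviations from the protocol will be recorded". No other section sets a general time for recording deviations.

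Section 8.4 introduces a list with "Specific reasons for discontinuing a subject for further assessments include", and one entry is "If there is a significant protocol deviation". The term significant is not defined. The same section adds: "The reason for subject discontinuation will be documented in the eCRF". It lets the sponsor keep data collected up to the point of discontinuation and hands later follow-up to the site's clinical routine.

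Section 10 fixes the time of outcome entry: "An eCRF will be filled out for all outcomes at the first postoperative visit, 30 days postop". Leak is part of that entry.

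Two kinds of departure have their own per-patient record. For the day-7 scan, Section 10.1.1 says: "If this CT is not performed (prior CT performed on clinical suspicion or other reason), this is specified". For analgesia, Section 9.5 says: "Escape (intervention group) or re-insertion (control group) of EDA can also be offered and should be recorded in the eCRF".

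Section 13.3 applies the ITT principle to all outcomes: operated patients are followed by randomized group whatever they actually received. It defines the per-protocol/safety set by comparing patients treated with epidural with those not so treated. On blinding, Section 9.1 says: "No blinding will be used during treatment".

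**The concern.** A rule that stops a subject's assessments because of a deviation works only if the deviation is identified while the subject is still being assessed. Apart from survival, that period ends at about day 30. Section 14.2 puts the recording at the end of recruitment, when for most patients there is little left to stop. A site cannot follow both sections as written.

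Two things are at stake. The first is the record of what was delivered. This is an open-label comparison of two techniques, and its reading depends on how many patients in each arm received the one allocated. If that is first listed at the end of inclusion, it is listed by people who already know who leaked. The second is completeness of the primary endpoint. If 8.4 is applied promptly, an operated patient with a deviation can leave assessment before day 30, whereas 13.3 requires that patient to be followed.

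**Working it through.** The point is about timing and consistency, so most of the check sets sections side by side.

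**1. 14.2 against 8.4.** 8.4 acts during participation; 14.2 records after the last inclusion. The only bridge is the discontinuation reason in the eCRF, which covers deviations that led to discontinuation and no others.

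**2. What is known when 14.2 applies.** Leak is entered at day 30, with a window of days 28 to 35 (Section 7.2). At the end of inclusion it is therefore known for all but patients operated on in roughly the last month.

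**3. Length of the delay.** The inclusion period is not stated. Assume that the last patient gets the full five years of survival follow-up by Q3 2033 and that inclusion starts in Q3 2026:
- last inclusion: Q3 2033 − 5 years = Q3 2028
- delay for the first patients: Q3 2028 − Q3 2026 = about 2 years
- delay for the last patients: close to none.

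**4. What is captured per patient anyway.**

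| Departure | Listed item |
|---|---|
| Day-7 CT not done | Yes, 10.1.1 |
| Rescue or re-insertion of epidural | Yes, 9.5 and 10.1.2 |
| Inadequate sensory block | Yes, 10.1.2 |
| Reason for discontinuation | Yes, 8.4 |
| Allocated epidural never placed | Indirect only: 10.1.3 records its start as early or late |
| Allocated block not given | None |

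The fifth row decides membership of the epidural-treated group in 13.3. The sixth does not change that membership, but without it the group not treated with epidural may contain patients who received neither technique.

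**5. 8.4 against 13.3.** For an operated, consenting patient with a deviation, 8.4 permits assessments to stop and 13.3 requires follow-up. Both cannot hold.

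**6. Effect on the figures.** The planned size reproduces with the unpooled formula: (1.960 + 0.842)² × (0.15 × 0.85 + 0.075 × 0.925) / 0.075² = 7.849 × 35 = 274.7, that is 275 per group. Nothing here changes it.

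For the 8.4 route, suppose that one leak patient in the intervention arm is discontinued before day 30 and drops out of the comparison. The counts are assumptions, and p is from the uncorrected chi-square test:
- planned rates (0.15 × 275 ≈ 41; 0.075 × 275 ≈ 21): 41/275 vs 21/275, p = 0.007; after removal 41/275 vs 20/274, p = 0.005
- a borderline result: 41/275 vs 26/275, p = 0.0505; after removal 41/275 vs 25/274, p = 0.037.

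One patient matters only near the threshold. Losing a control-arm leak would push the other way.

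**The case against.** The strongest reply is that 14.2 can be read as a compilation step before database lock. It does not say that nothing is recorded earlier. A reader might infer that deviations are recorded solely at the end and rebuilt from memory. The protocol does not support that: step 4 shows several departures entered per patient, and Section 15 has a monitor visiting during the trial to check compliance. This part of the reply stands.

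A reader might also infer that late listing biases the primary result. It does not do so directly. A deviation first listed at the end of inclusion cannot undo a leak already recorded, data collected before discontinuation are kept, and no set in 13.3 is built from a deviation list. Any threat to leak ascertainment comes from discontinuation before day 30, which is a fault of 8.4 rather than of the timing in 14.2.

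Two further inferences fail. Knowledge of allocation is not a consequence of late recording, because in an open-label trial the site knows the arm at any time. Nor can one say that the data monitoring committee would be left uninformed: Section 12 gives it complications and other outcomes by arm, and epidural rescue or re-insertion is among the listed outcomes.

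What the reply does not answer is that 14.2 states a time and 8.4 needs an earlier one, that 8.4 and 13.3 give opposite instructions for the same patient, and that delivery of the allocated technique has no direct item.

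**Conclusion.** The point holds as an inconsistency among three sections plus a gap in what is recorded. It is modest in size. Sample size, power, alpha and the ITT analysis as defined are untouched by late listing. The practical losses are a record of technique delivery made after leak status is known, which bears on the per-protocol/safety set and on adherence by arm, and possible loss of day-30 leak data if 8.4 is applied as written.

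The delay of up to about two years rests on the date assumption in step 3. The p-values in step 6 rest on assumed counts; they show when a single lost patient could matter, not that one will be lost. Nothing in the protocol says that deviations will be judged in the light of the outcome. The case for change is that the text permits this, that a record made at the time cannot be recovered afterwards, and that the trial is planned to start in Q3 2026.

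**What to change.** - **Section 14.2:** state that deviations are recorded in the eCRF as they occur. Keep the end-of-inclusion step only as a check before lock.
- **eCRF:** add an item for delivery of the allocated technique (block given or not; epidural placed or not), entered at or just after surgery. Waiting for the day-30 form would not serve, because leak is entered on that same form.
- **Classification:** define significant, and have deviations classified before lock from listings that omit leak status.
- **Section 8.4:** state that a protocol deviation does not by itself end the day-30 leak assessment of an operated patient who still consents. This concerns data collection only and brings 8.4 into line with 13.3.

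The cost is a few sentences, a few eCRF fields and slightly more data entry around surgery. Sites will still know the arm when they record, and this change cannot remove that.

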## 14.3 Direct access to source data/documents

The Investigators will permit trial-related monitoring and audits, providing access to source data. The Sponsor verifies that each subject has consented in writing to direct access to the original source data by the use of written subject information and signed Informed Consent.

During the monitoring, the data recorded in the eCRFs by the Investigator will be controlled for consistency with the source data/hospital records by the independent trial monitor (source data verification). Any discrepancies in data will be documented and explained in the monitoring reports.

## 14.4 Quality control and quality assurance

The principal investigator will arrange bi-annual trial meetings in conjunction with the Scandinavian esophagogastric cancer (SECGC) meetings. This will ensure that the local investigators are adequately informed about the protocol and that data input and storage are according to protocol.

## 14.5 Source data

The following minimum amount of information should be recorded in the hospital records:

- Trial ID
- Subject identification.
- Date when subject information was given and when signed Informed Consent was obtained.
- Diagnosis.
- Fulfillment of inclusion criteria.
- Specification of visit dates, concomitant medication
- Specification of the subject's cessation in the trial (e.g., completer or premature withdrawal).
- Specification of the subject's outcome in the trial.

## 15 Monitoring

Monitoring of the trial will be arranged by the Sponsor. During the trial, the Monitor will have regular contacts with the trial sites, including visits to ensure that the trial is conducted and documented properly in compliance with the protocol and applicable regulatory requirements.

The Monitor will review source documents for verification of consistency with the data recorded in the eCRFs. The Monitor will also provide information and support to the Investigators.

The Investigator should provide a curriculum vitae (CV) or equivalent documentation of suitability to be responsible for the trial. All Investigators and other responsible personnel should be listed together with their function in the trial on the signature list.

Trial ID:	ISRCTN16853684
Version No:	1.0
Date:	January 27 th 2026

## 15.1 Audits

Authorized members of the study group can perform audits at the sites included in the study. The purpose of these audits is to ensure adherence to the study protocol. The local representative is responsible for secure storage of the original consent forms.

# 16 Ethics

## 16.1 Ethical conduct of the trial

The trial will be conducted in accordance with the protocol, applicable regulatory requirements, and the ethical principles of the Declaration of Helsinki as adopted by the 18th World Medical Assembly in Helsinki, Finland, in 1964 and subsequent versions.

## 16.2 Ethical review of the trial

The final version of the trial protocol and subject information must be approved by the Ethical Review Authority of the countries involved in the trial, before the trial can start. The Ethical authorities will also be informed of any changes in the trial protocol or subject information in accordance with current requirements.

## 16.3 Subject information and informed consent

It is the responsibility of the Investigator to provide each subject with full and adequate verbal and written information about the objectives, procedures, and possible risks and benefits of the trial. All subjects will be given the opportunity to ask questions about the trial and will be given sufficient time to decide whether or not to participate in the trial. The written subject information must not be changed without prior discussion with the Sponsor.

The subjects will be notified of their voluntary participation and of their freedom to withdraw from the trial at any time and without giving any particular reason. Subjects must also be informed that withdrawing from the trial will not affect their future medical care, treatment or benefits to which the subject is otherwise entitled.

The Investigator is responsible for obtaining written Informed Consent from all subjects prior to enrolment in the trial.

The subjects will consent to:

- Participating in the trial.
- Sponsor representatives gaining full access to hospital records, to verify the accuracy of the data collected in the trial.
- Recording, collecting, and processing of data and storing of data in a database.

It should be clearly stated that the data will not identify any subject taking part in the trial, in accordance with the Regulation (EU) 2016/679 (General Data Protection Regulation, GDPR).

Trial ID: ISRCTN16853684  
Version No: 1.0  
Date: January 27th 2026

A copy of the subject information and the Informed Consent form will be given to the subject. The Investigator (or the designated representative) who gave the verbal and written information to the subject will sign the Informed Consent form. The Investigator will file the signed Informed Consent forms in the Investigator's File for possible future audits and inspections.

## **17 Insurance**

All subjects are insured according to national regulations, either by national patient and pharmaceutical insurance or local insurance at the participating center. Subjects enrolled in Sweden are insured through the Swedish Patient Insurance (Landstingens Ömsesidiga Försäkringsbolag).

## **18 Notification of trial completion, reporting, and publication**

After completion of the trial, the statistical analyses will be performed by the Sponsor, and the results will be presented to the Investigators. The results will form the basis for a manuscript intended for publication in a scientific peer-reviewed journal.

Trial ID: ISRCTN16853684  
Version No: 1.0  
Date: January 27th 2026

### **Numeric Rating Scale (NRS)**

Associate a number from **0** (no pain) to **10** (maximum imaginable pain): ...../10

## Appendix 2

### QoR-15 Patient Survey

Date: \_\_\_/\_\_\_/\_\_\_

Study #: \_\_\_\_\_

Preoperative

Postoperative

#### PART A

##### *How have you been feeling in the last 24 hours?*

(0 to 10, where: 0 = none of the time [poor] and 10 = all of the time [excellent])

1. Able to breathe easily	None of _____ the time	0	1	2	3	4	5	6	7	8	9	10	All of the time
2. Been able to enjoy food	None of _____ the time	0	1	2	3	4	5	6	7	8	9	10	All of the time
3. Feeling rested	None of _____ the time	0	1	2	3	4	5	6	7	8	9	10	All of the time
4. Have had a good sleep	None of _____ the time	0	1	2	3	4	5	6	7	8	9	10	All of the time
5. Able to look after personal toilet and hygiene unaided	None of _____ the time	0	1	2	3	4	5	6	7	8	9	10	All of the time
6. Able to communicate with family or friends	None of _____ the time	0	1	2	3	4	5	6	7	8	9	10	All of the time
7. Getting support from hospital doctors and nurses	None of _____ the time	0	1	2	3	4	5	6	7	8	9	10	All of the time
8. Able to return to work or usual home activities	None of _____ the time	0	1	2	3	4	5	6	7	8	9	10	All of the time
9. Feeling comfortable and in control	None of _____ the time	0	1	2	3	4	5	6	7	8	9	10	All of the time
10. Having a feeling of general well-being	None of _____ the time	0	1	2	3	4	5	6	7	8	9	10	All of the time

